4.2. Fitzpatrick Wrinkle Classification Scale (FWCS)

Assessment of subject wrinkles will be performed by the Investigator and in addition, will be performed by three board-certified independent dermatologists or plastic surgeons ("Raters"), using the Fitzpatrick Wrinkle Classification Scale (FWCS) categories as shown in Table 4. The FWCS is a clinically validated assessment tool used to assess skin wrinkle severity and elastosis on a scale from 1 through 9, where the lower score is considered better.

The investigator will assess FWCS at baseline, 1-months and 3 months follow up visit, while the raters will assess only at baseline and 3 months follow up visit.

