6.3. Endpoints for Analysis

6.3.1. Primary Efficacy Endpoint

The primary efficacy endpoint is the comparison of the proportion of subjects (i.e. percentage of treatment responders) with a ≥ 1 -score improvement on the FWCS at the 3- month visit, as compared to baseline as determined by at least 2 out of 3 blinded Independent Photographic Reviewers. The study design assumes a 65% success rate of subjects with treated wrinkles with a ≥ 1 -score change on the FWCS; therefore, even or greater than 65% of subjects must be rated with a ≥ 1 -score improvement 3 months after treatment. and must be statistically significantly.

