6.4.3. Handling of Missing Data

- Every effort will be made to obtain all FWCS data at month-3 evaluation from all subjects who have been enrolled to minimize missing data. However, in the event when there is missing data the following imputation methods will be used.
- Imputation using mean values: the missing FWCS value will be replaced by the average of non-missing FWCS values at month-3 in the same treatment group by the same evaluator.
- Imputation using baseline values: the missing FWCS value will be replaced by the subject's baseline FWCS value by the same evaluator.
- The MMRM model (Mixed-effect Model for Repeated Measures), which is based on MAR (missing at random) assumption will be applied to all enrolled subjects.

Sensitivity analyses will be applied for testing the effect of the imputation on the treatment effect. This will show the influence of the imputation on the study results.

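### The one missing-at-random method in section 6.4.3, an MMRM, cannot deliver the all-enrolled check on the primary responder rate; the per-protocol result itself is unaffected

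*Combined protocol and SAP*

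**What the plan says.** Section 6.4.3 gives three ways to handle a missing month-3 FWCS:

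- **Mean imputation:** "the missing FWCS value will be replaced by the average of non-missing FWCS values at month-3", within the same group and evaluator.
- **Baseline-value imputation:** "the missing FWCS value will be replaced by the subject's baseline FWCS value by the same evaluator".
- **An MMRM**, "which is based on MAR (missing at random) assumption will be applied to all enrolled subjects".

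Only the third is described as MAR-based. The section does not say whose scores enter the model, what covariates or covariance structure it has, or how its output becomes a responder status. It also promises sensitivity analyses of the effect of imputation.

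Section 4.2 fixes the scoring times. For the investigator: "The investigator will assess FWCS at baseline, 1-months and 3 months follow up visit". For the blinded raters: "the raters will assess only at baseline and 3 months follow up visit". The flowchart in section 3 agrees, with the blinded assessment marked at Visits 1 and 6 only.

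Sections 1.7.1 and 6.3.1 define the primary endpoint as a proportion, the "percentage of treatment responders", where response is an improvement of at least one point according to at least 2 of 3 raters. The proportion is set against 65%. Section 6.2.2 places the primary efficacy analysis on the per-protocol set (PPS), which needs the full course of treatments and usable images at baseline and month 3.

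**The concern.** An MMRM handles dropout by borrowing from a subject's own earlier post-baseline measurements. The raters provide none, so the method has almost nothing to borrow. What it returns is also on a different scale from the primary endpoint.

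The PPS leaves out everyone without month-3 images. Section 6.4.3 is the plan's only stated check on that exclusion. If subjects who do poorly are lost more often, an all-enrolled analysis that essentially repeats the completer result would look like reassurance without testing anything. Section 6.1 allows for up to 15% attrition, enough for the lost subjects to decide which side of 65% the result falls on.

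**Working it through.** **1. The plan's own figures (section 6.1).** Half-width = 1.96 × √(0.65 × 0.35 / 44) = 0.141, against 0.14 stated. Enrolment: 44 × 1.15 = 50.6, rounded up to 51, as stated (44 / 0.85 would give 52). So 44 evaluable of 51 leaves 7 missing.

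**2. What 7 missing can do.** Suppose 29 of 44 completers respond: 29/44 = 65.9%. Over all 51 the rate lies between 29/51 = 56.9% (all missing fail) and 36/51 = 70.6% (all missing succeed). The range spans 65%.

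**3. What an MMRM does with one post-baseline score.** One data set was simulated with assumed values: 51 subjects, integer scores, 7 missing at month 3.

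| Analysis | Mean improvement |
|---|---|
| Completers, unadjusted | 0.932 |
| Regression on baseline, at the completers' mean baseline | 0.932 |
| Regression on baseline, at the mean baseline of all 51 | 0.937 |
| Maximum likelihood with baseline as a second response | 0.937 |

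The baseline-only subjects move the estimate by 0.005 points. No post-baseline information comes from them.

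**4. A mean does not determine the responder share.** Take change as Normal(1.0, SD) and count a response when it rounds to 1 or more. The share is then Φ(0.5/SD), where the SDs are assumptions:

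- SD 0.8: Φ(0.625) = 73%
- SD 1.2: Φ(0.417) = 66%
- SD 2.0: Φ(0.25) = 60%

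The same mean falls on either side of 65%.

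**5. Possible size under informative dropout.** 3,000 simulated trials of 51 subjects. Assumptions: true change N(1, 1); rater error SD 0.5 on the change; investigator's 1-month change = 0.8 × true change + N(0, 0.6), rounded; loss 28% if that 1-month change is 0 or less and 5% otherwise (13.8% overall).

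| Estimate | Responder rate |
|---|---|
| Full data | 68.2% |
| Completers | 71.5% |
| Missing set to baseline, so non-responder: 71.5% × (1 − 0.138) | 61.6% |
| Stratified by the investigator's 1-month change | 68.3% |

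Mean change was 1.002 in full data, 1.084 in completers and 1.084 from the one-occasion MMRM. With milder selection (22% against 8%) the full, completer and stratified rates were 68.1%, 70.0% and 68.1%.

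**6. When the extra information exists.** Treatments are four weeks apart. Visit 4 is therefore at about week 12, Visit 5 at about week 16 and Visit 6 at about week 24. After baseline, investigator FWCS and GAIS are scheduled only at Visits 5 and 6. If part of the loss in step 5 occurs before Visit 5, the stratified estimate drifts back to the completer value:

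| Share of losses before Visit 5 | Estimate |
|---|---|
| 0% | 68.3% |
| 50% | 69.9% |
| 75% | 70.6% |
| 100% | 71.5% |

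**The case against.** Four points can be made for the plan.

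- **The primary result does not use the MMRM.** This stands. Because the PPS requires images at both visits, it should contain almost no missing rater scores. A reader might infer that the headline result is biased by the choice of MMRM; section 6.2.2 does not support that. The fault is confined to the all-enrolled analysis.
- **The plan already tests for loss of non-responders.** This stands in part. Baseline-value imputation gives a lost subject zero change, hence non-response, and works directly with the 2-of-3 rule. In the simulation it gave 61.6%, so it and the completer rate (71.5%) bracket the full-data 68.2%. It would be wrong to say that the plan has no protection. But this is a deliberately pessimistic analysis, not an MAR one. Mean imputation does not fill the gap: it makes a lost subject's response depend only on whether the baseline score exceeds the month-3 average by a point.
- **The MMRM may be meant for the investigator's FWCS.** The text permits this, and with 1-month and 3-month scores the method would suit. The primary endpoint would then have no MAR analysis at all, so the section would still need changing.
- **The simulated correction is built in.** This stands. Loss was made to depend only on the 1-month score, every lost subject was given one, and the estimate conditioned on it. Change was also simulated without any relation to baseline, so exact agreement of the MMRM with completers was guaranteed there. Step 3 shows that the agreement is approximate in general.

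**Conclusion.** The point holds for the all-enrolled sensitivity analysis of the primary endpoint. As written, the only MAR-labelled method takes no post-baseline rater information from lost subjects and yields a mean that cannot be set against 65%. Both conclusions follow from sections 4.2, 6.3.1 and 6.4.3 and need no simulation. What is lacking is a valid MAR counterpart to the conservative imputation that the plan already has.

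The size is less certain. The range from 56.9% to 70.6% is arithmetic on an illustrative 29 of 44. The move from 71.5% to 68.3% is a best case under an assumed dropout mechanism, and it was obtained with a stratified rate rather than the multiple imputation recommended here. A reader might infer that the remedy would remove dropout bias. The visit schedule does not support that for anyone lost before Visit 5. This is a change that should be made, but the primary per-protocol conclusion does not turn on it.

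**What to change.** In section 6.4.3, for the primary endpoint in all treated subjects (the FAS), replace the MMRM with multiple imputation:

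1. Impute each rater's missing month-3 score from that rater's baseline score and, where available, the investigator's FWCS (baseline, 1 month, 3 months) and 1-month GAIS.
2. Apply the 2-of-3 rule in each completed data set.
3. Pool the proportions by Rubin's rules.
4. Report the result beside the baseline-value (non-responder) imputation.

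Keep the MMRM for the investigator's mean FWCS, and say that this is its purpose.

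The cost is SAP wording and a little programming, using assessments already scheduled. Two limits should be written into the plan. Subjects lost before Visit 5 have no post-baseline FWCS or GAIS, so their imputation rests on baseline alone and the non-responder analysis is the main safeguard. With about 44 completers, the imputation model must stay small.

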6.4.4. Data Collection

Subject demographic information, procedural data, adverse events, device observations, and study required assessments will be documented on the CRFs. Study subjects will complete Visual Analog Scale (VAS) and Downtime assessment following each treatment visit and Experience questionnaire at each follow-up visit.

6.5. Confidentiality of Data

The Principal Investigator will oversee the conduct of the study and all data will be kept confidential. Confidentiality will be maintained by using subject identification numbers instead of names. Informed consent forms, data collection sheets and records, linking a subject's name with their ID number will be maintained in a locked cabinet or locked office. Information to be stored on the computer will be identified by subject ID and will be password protected. Data disclosed outside the study team will be de-identified or will only include general group demographic information. Protected Health Information and/or identifiable study data will not be shared with anyone outside the study team or Health System, with the exception of the study sponsor, and federal regulators/ institutional officials for the purposes of auditing.
